10.3 Assessments

10.3.1 Efficacy Variables

Efficacy will be assessed by daily average pain, as measured on an 11-point (0-10) NRS; the Galer NPS the DSIS; the PGIC; and the SF-36. The time points for each assessment are listed in Schedule of Events (Table 2-1).

10.3.1.1 Numerical Rating Scale

Subjects will assess their perceived average neuropathic pain over the previous 24 hours using an 11-point NRS, with 0 representing no pain and 10 representing the worst pain imaginable. Subjects will be instructed to assess their average daily pain at approximately the same time every morning, and to record their response in a subject diary (ePRO).

10.3.1.2 Galer Neuropathic Pain Scale

Subjects will assess their neuropathic pain using the Galer NPS. The NPS includes 2 descriptors of pain, including intensity and unpleasantness, and 8 descriptors that assess specific qualities of neuropathic pain: sharp, hot, dull, cold, sensitive, itchy, deep, and surface pain. Each of these 10 dimensions has a 0 to 10 NRS in which 0 is equal to no pain and 10 equals the most intense pain.

10.3.1.3 Daily Sleep Interference Scale

Subjects will assess how their neuropathic pain interferes with their sleep using the DSIS. The DSIS is an 11-point Likert scale, with 0 indicating that pain did not interfere with sleep and 10 indicating that pain completely interfered with sleep. The DSIS is completed by subjects once a day (upon awakening) to accurately capture variability in sleep interference due to pain on a daily basis, thus minimizing recall bias.

734 of 938 Page 61 of 114

10.3.1.4 Patient Global Impression of Change

Subjects will rate their overall improvement in health status using the PGIC. The PGIC consists of a 7-point scale where 1 = "very much improved" and 7 = "very much worse". Subjects will be asked the following question: "How would you rate your overall improvement with treatment during the clinical study?" The response options include the following:

Very Much Improved	1
Much Improved	2
Minimally Improved	3
No Change	4
Minimally Worse	5
Much Worse	6
Very Much Worse	7

10.3.1.5 Short-Form Health Survey

The subject's health status and quality of life will be assessed using the SF-36.

The SF-36 assesses 8 health concepts: 1) limitations in physical activities because of health problems; 2) limitations in social activities because of physical or emotional problems; 3) limitations in usual role activities because of physical health problems; 4) bodily pain; 5) general mental health (psychological distress and well-being); 6) limitations in usual role activities because of emotional problems; 7) vitality (energy and fatigue); and 8) general health perceptions. The items use Likert-type scales with either 5 or 6 points, or 2 or 3 points.

10.3.1.6 Rescue Medication Use

Subjects will record all rescue medications they take for neuropathic pain in a paper diary.

10.3.2 Clinical Pharmacology

Samples will be collected at the time points specified in the Schedule of Events (Table 2-1).

10.3.2.1 Pharmacokinetic Analysis Methods

The PK characterization of drug concentrations for each dose to be profiled will use noncompartmental analysis (NCA). Standard PK parameters assessed will include measures of the extent of absorption using estimates of the area-under-the-curve (AUC) and rate-of-absorption using the C_{max} and T_{max} . The following PK parameters will be determined:

- Maximum plasma concentration (C_{max})
- Time to maximum plasma concentration (T_{max})
- Apparent first order terminal elimination half-life ($t\frac{1}{2}$)
- Area under the plasma concentration-time curve from time 0 to the time of the last quantifiable plasma concentration (AUC_{0-t})
- Area under the plasma concentration-time curve from time 0 to infinity (AUC $_{0-\infty}$)
- AUCtau at steady state
- C_{max} at steady state
- Volume of distribution at steady state
- Apparent total body clearance at steady state (CL_{ss})

Actual sampling times will be used for all PK parameter estimation.

Additional details of the parameters and their calculation and evaluation will be included in the SAP.

10.3.2.2 Pharmacodynamic Variables

Plasma or serum samples will be collected for exploration of free and/or total NGF.

10.3.2.3 Pharmacogenetic Variables

Pharmacogenetic analysis is optional. If a subject declines to participate in the genetic research, this will have no influence on the ability of the subject to participate in the study.

Samples will be analysed using a validated analytical method in compliance with AstraZeneca's standard operating procedures and analytical requirements.

CC

10.3.2.5 Immunogenicity

Blood samples will be collected for assessment of ADA levels.

10.3.3 Safety Variables

Safety assessments will include the evaluation of AEs, clinical laboratory tests, vital signs, 12-lead ECGs, physical and neurological examination findings, neuropathy assessments (TNSn), strength (dorsiflexion), and deep tendon reflex (knee and ankle) assessments, motor and sensory nerve conduction, concomitant medications, injection site reactions, and infusion reactions.

10.3.3.1 Clinical Laboratory Assessments

10.3.3.1.1 Clinical Laboratory Tests to be Performed

Samples for laboratory tests will be collected at the time points specified in the Schedule of Events (Table 2-1) and will include the following:

Haematology: hemoglobin, haematocrit, red blood cell (RBC) count, RBC indices, mean

corpuscular hemoglobin, mean corpuscular hemoglobin concentration, platelet count (or estimate), white blood cell count including differential

Serum Chemistry: albumin, total bilirubin, total protein, calcium, ALP, ALT, AST, blood

urea nitrogen, creatinine*, glucose, sodium, potassium, chloride, bicarbonate, lactate dehydrogenase, uric acid, C-reactive protein (CRP)

*serum chemistry reports should include calculation of creatinine clearance using the Cockcroft-Gault equation for estimation of GFR

(eGFR)

Coagulation Panel: prothrombin time, partial thromboplastin time, fibrinogen

Urinalysis: pH, specific gravity, blood urine, glucose, protein, ketones

Pregnancy Test

for women who are not surgically sterile

[urine]:

Urine Drug Screen: including but not limited to amphetamine, barbiturate, cannabinoids,

cocaine, methadone, methaqualone, opiate, phencyclidine, and

propoxyphene

Serology: HIV, hepatitis B and C, and tuberculosis (QuantiFERON)

Blood and urine samples for haematology, serum chemistry, urinalysis, and serology will be sent to a central laboratory for analysis. Urine drug screens and pregnancy tests will be conducted at the study sites.

AD-MW-07.06 08-Dec-2017 737 of 938 Page 64 of 114

10.3.3.1.2 Specimen Handling Requirements

The transmission of infectious agents may occur through contact with contaminated needles and blood or blood products. Consequently, appropriate blood and body fluid precautions should be employed by all study personnel involved in the collection of blood and handling of specimens in both the clinic and laboratory settings. Refer to current recommendations of the appropriate authorities.

In addition to appropriate handling of subject samples, specific regulations exist regarding the shipment of biologic/etiologic samples. Procedures and regulations for the packaging and shipping of infectious samples are outlined in the study manual. The investigator is responsible for ensuring that all study samples that are to be transported to another location are packed and shipped appropriately according to the applicable regulations.

10.3.3.1.3 Evaluation of Clinical Laboratory Values

The normal ranges of values for the clinical laboratory assessments in this study will be provided by the responsible laboratory and submitted to AstraZeneca prior to the beginning of the study. They will be regarded as the reference ranges on which decisions will be made.

If a laboratory value is out of the reference range, it is not necessarily clinically relevant. The investigator must evaluate the out-of-range values and record his or her assessment of the clinical relevance in the appropriate CRF/eCRF.

All clinical laboratory values that in the investigator's opinion show clinically relevant or pathological changes during or after termination of treatment must be reported as AEs and followed, as described in Section 11.2.5.

All measurements described in this section are recognized standard methods.

10.3.3.1.4 Clinical Examinations

10.3.3.1.5 Vital Signs

Vital signs (HR, BP, respiratory rate, and temperature) will be measured after the subject has been in a supine position for 5 minutes at screening and Day 1 and in a sitting position for 5 minutes at all other visits. To assess orthostasis, BP and pulse will be measured again 1 minute (>1 minute, <3 minutes) after the subject stands.

Vital signs will be assessed as follows:

- Screening: Measure respiratory rate, temperature, and HR and BP after a 5-minute rest in **supine** position. To assess orthostasis, repeat BP and HR 1 minute after the subject stands.
- Day 1 pre-dose: Measure respiratory rate, temperature, and HR and BP after a 5-minute rest in **supine** position. To assess orthostasis, repeat BP and HR 1 minute after the subject stands.
- Day 1 post-dose: **Supine and orthostatic** BP and HR at 15 mins, 30 mins, 45 mins, 60 mins, 2 hours, and 4 hours after start of infusion. Temperature and **supine and orthostatic** BP and HR at 60 mins, 2 hours, and 4 hours after start of infusion. Respiratory rate at 15 mins, 60 mins, 2 hours, and 4 hours after start of infusion. The 60-minute assessments should be performed within 10 minutes of the end of the infusion. [Note: An acceptable window for these vital sign assessments is ± 5 mins in relation to the specified time.]

- Days 14, 28, 42, 56, and 70 pre-dose: Measure respiratory rate, temperature, and HR and BP after a 5-minute rest in **sitting** position. To assess orthostasis, repeat BP and HR 1 minute after the subject stands.
- Days 14, 28, 42, 56, and 70 post-dose: 5 minutes after completion of infusion, measure respiratory rate, temperature, and HR and BP after a 5-minute rest in **sitting** position. After measuring sitting vital signs, assess orthostatic BP and HR 1 minute after the subject stands
- Days 71, 77, and Week 18 or early termination: Measure respiratory rate, temperature, and HR and BP after a 5-minute rest in **sitting** position. To assess orthostasis, repeat BP and HR 1 minute after the subject stands.

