Abbreviations: ADA = anti-drug antibody; BMI = body mass index; C = complete; CCI

; DSIS = Daily Sleep Interference Scale; ECG = electrocardiogram; ePRO = electronic patient-reported outcome system;

IP = investigational product; IWRS = interactive web response system; CCI NRS = numeric rating scale;

PD = pharmacodynamics; PGIC = Patient Global Impression of Change; PK = pharmacokinetics; SF-36 = 36-item Short-Form Health Survey;

T = targeted; TNSn = Total Neuropathy Score-Nurse

- a The subject must be screened within 45 days before enrolment in the study and at least 7 days before the first day of treatment to allow for 7 days of baseline pain ratings and sleep monitoring. Screening procedures may be performed at 1 or more visits. If the screening urine pregnancy test is more than 7 days before the first day of treatment, it must be repeated prior to the first dose. Urine drug screen tests will be performed at Screening only.
- b On Day 1, 12-lead ECGs (3 replicates) will be performed pre-dose; 60 (±10) minutes after start of IP administration; and 2 and 4 hours (±10 minutes) after start of IP administration.

- c Vital signs (heart rate [HR], blood pressure [BP], respiratory rate, and body temperature):
 - Screening and Day 1: Supine and orthostatic.
 - From Day 14 onwards: Sitting and orthostatic.

CCI

e If necessary, the randomisation transaction in IWRS can be performed on Day -1.

CCI

i Strength (dorsiflexion) and deep tendon reflexes (knee and ankle) are to be scored at every visit alongside the TNSn assessments.

CCI

Table 2-2: Timing of Safety Assessments and Safety Blood Sampling on Day 1

			Т	ime after S	Start of IP	Administra	tion	
Assessment	Pre-dose	0 min	15 mins	30 mins	45 mins	60 mins	2 hours	4 hours
Administration of IP		-						
Injection site assessments and infusion reaction assessments			X	X	X	X	X	X
12-lead ECGs (3 replicates)	X					X	X	X
Supine blood pressure, heart rate	X		X	X	X	X	X	X
Standing (orthostatic) blood pressure, heart rate	X					X	X	X
Body temperature	X					X	X	X
Respiration rate	X		X			X	X	X
Total Neuropathy Score, nurse (TNSn)	X							
Targeted physical and neurological exam	X							
Adverse events	4							
Safety laboratory tests	X							
Concomitant medication use	4							

Abbreviations: BP = blood pressure; ECG = electrocardiogram; HR = heart rate; IP = investigational product, mins = minutes; RR = respiratory rate; TNSn = Total Neuropathy Score-Nurse

Note:

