5.3 Summary of Potential Risks and Benefits

The potential benefits of study participation are that subjects with PDN may experience a reduction in symptoms as a result of treatment with MEDI7352. No other benefits of participation are anticipated.

The potential risks of study participation include those associated with exposure to MEDI7352, as well as those related to medical procedures, including venepuncture undertaken for blood sampling and administration of investigational product (IP). Although no important risks have been identified for MEDI7352 to date in the completed Phase 1 clinical study or the 3 ongoing studies, MEDI7352 may have risks similar to those reported with both anti-NGF and anti-TNF therapies, as well as those reported with therapeutic proteins in general.

Potential risks associated with MEDI7352 include:

- Potential risks based on class effects and mechanisms of action
 - o Risks associated with the anti-NGF mechanism
 - Rapidly progressive OA and other joint safety events. This risk is not limited to osteoarthritic joints
 - Sensory abnormalities and peripheral neuropathy
 - Autonomic neuropathy and sympathetic dysfunction
 - o Risks associated with the anti-TNF mechanism
 - Increased risk of infection, including tuberculosis, bacterial sepsis, and invasive fungal infections
 - Warnings and precautions for etanercept (anti-TNFα therapy) include hypersensitivity reactions; exacerbation or new onset of demyelinating disease; malignancies, including lymphoma, leukaemia, melanoma and non-melanoma skin cancer; serious haematological reactions including pancytopenia, or aplastic anaemia; new onset or worsening congestive heart failure; reactivation of hepatitis B; autoimmune conditions including autoimmune hepatitis, autoimmune renal disease and a lupus-like syndrome (ENBREL Prescribing Information, ENBREL Summary of Product Characteristics).

• General risks associated with protein therapeutics include immunological reactions: hypersensitivity reactions, injection site reactions, and the consequences of immunogenicity (eg, immune-complex disease).

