- 22. Within 1 year of screening or between screening and randomisation, any of the following: myocardial infarction, hospitalisation for unstable angina or arrhythmia, or unexplained syncope.
- 23. Clinically important infection, including chronic, persistent, or acute infection, within **3 months** of screening or between screening and randomisation.
- 24. Current serious or unstable clinically important illness, including avascular necrosis, respiratory, cardiovascular, gastrointestinal, endocrinologic (excluding well-controlled type 1 or type 2 diabetes), immunologic, haematologic, neurologic, or other major disease that is likely to deteriorate or affect the subject's safety or ability to complete the study, as judged by the investigator.

Procedural contraindications

25. Any significant medical or surgical procedure or trauma within 28 days of Day 1, or planned to be undertaken within the timeframe of the clinical trial, that will likely affect the subject's safety or ability to complete the study, or the scientific integrity of the study data, as judged by the investigator.

Physical and neurological examination, vital signs, ECG, laboratory values, and imaging

- 26. Clinically important abnormality in the physical and neurological examination, vital signs, or clinical laboratory test at screening that could affect the subject's safety or ability to complete the study, or the integrity of the clinical trial data, as judged by the investigator.
- 27. Poorly controlled hypertension (defined as systolic blood pressure [SBP] of >165 mmHg and/or diastolic blood pressure [DBP] of >95 mmHg measured in the clinic) or orthostatic hypotension (defined as a sustained reduction of SBP of at least 20 mmHg and/or a DBP reduction of at least 10 mmHg within 3 minutes of standing from a supine position). Note: If the blood pressure (BP) measured in the clinic is out of range, the measurements can be repeated on the same day or at another convenient visit.
- 28. Prolonged QTcF of >470 msec or family history of long QT syndrome, or shortened QTcF of <360 msec or family history of short QT syndrome, or any clinically significant abnormality in ECG rhythm, conduction, or morphology, including but not limited to:
 - PR/PQ interval prolongation (PR/PQ >220 ms)
 - intermittent second or third degree atrioventricular (AV) block (AV block II Mobitz Type I, Wenckebach, while asleep or in deep rest is not exclusionary)

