10.2.2.2 Days 14, 28, 42, 56, and 70 (Treatments 2 to 6)

The following procedures will be performed on Days 14, 28, 42, 56, and 70:

- 1. Perform Galer Neuropathic Pain Scale (NPS) (Days 28 and 56 only).
- 2. Perform PGIC (Days 28 and 56 only).
- 3. Perform a targeted physical and neurological examination.
- 4. Perform TNSn, strength (dorsiflexion), and deep tendon reflex (knee and ankle) assessments.
- 5. Perform 3 replicates of 12-lead ECGs (with printouts) after the subject has been resting in the supine position for at least 10 minutes (Days 28 and 56 only).
- 6. Measure pre-dose sitting vital signs (HR, BP [sitting after a 5-minute rest], respiratory rate, and temperature). To assess orthostasis, repeat the measurement of BP and pulse 1 minute (>1 minute, <3 minutes) after the subject stands.
- 7. Collect pre-dose blood samples for the following:
 - chemistry, haematology, and coagulation
 - immunogenicity (ADA) testing (Days 14, 28, 56, and 70 only)
 - CCI
 - PK
- 8. Collect urine sample for the following:
 - urinalysis

9. Administer the IP infusion.

CCI

- 11. Five (5) minutes (± 5 minutes) after completion of the infusion, repeat sitting vital signs (HR, BP [sitting after a 5-minute rest], respiratory rate, and temperature). Orthostatic vital signs (standing heart rate and BP) should be measured at 5 minutes (± 5 mins) after completion of the infusion. These orthostatic measurements should be taken after the sitting measurements and after the subject has adopted the standing position for 1 minute (>1 minute, <3 minutes).
- 12. Assess the IV injection site for local reactions.
- 13. Approximately 8 hours (\pm 15 mins) after the start of the infusion, collect a blood sample for the following (**Day 70 only**):
 - PK
 - CCI
 - CCI
- 14. Record AEs and concomitant/rescue medications and therapies.

- 15. Remind the subject to continue entering their daily pain and DSIS into the ePRO system and rescue medication into the paper diary.
- 16. Schedule the subject to return to the clinic for the next visit (on Day 70, schedule the subject to return to the clinic for the 24-hour blood sample).

10.2.2.3 Day 71

- 1. Measure sitting vital signs (HR, BP [sitting after a 5-minute rest], respiratory rate, and temperature). To assess orthostasis, repeat the measurement of blood pressure and pulse 1 minute (>1 minute, <3 minutes) after the subject stands.

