13.1.6.3 Vital Signs

Descriptive summaries (mean, SD, median, minimum, and maximum) of actual values and changes from baseline will be calculated for SBP, DBP, HR, respiratory rate, and temperature.

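### Resting blood pressure and heart rate are taken supine before treatment but sitting at all nine visits after Day 1, so later changes from baseline mix postures and no seated baseline exists

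*Protocol*

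**What the plan says.** The posture rule is stated consistently throughout the protocol. Section 10.3.3.1.5 has vital signs taken "in a supine position for 5 minutes at screening and Day 1 and in a sitting position for 5 minutes at all other visits". Footnote c to the Schedule of Events (Section 2.2) agrees: "Screening and Day 1: Supine and orthostatic", then "From Day 14 onwards: Sitting and orthostatic". The visit procedures in Sections 10.2.1.1 to 10.2.3 follow the same split. At every visit a standing reading follows: "To assess orthostasis, BP and pulse will be measured again 1 minute (>1 minute, <3 minutes) after the subject stands".

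For analysis, Section 13.1.6.3 plans descriptive summaries in which "actual values and changes from baseline will be calculated for SBP, DBP, HR, respiratory rate, and temperature". It does not mention posture.

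Two other places bear on the point. Section 5.3 lists "Autonomic neuropathy and sympathetic dysfunction" among the potential risks of the anti-NGF mechanism. Exclusion criterion 27 (Section 8.2.2) defines orthostatic hypotension by a fall in pressure "within 3 minutes of standing from a supine position".

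**The concern.** A change from baseline can be read as a change in the subject only if both readings are taken under the same conditions. Here the resting posture changes between the last pre-treatment reading and the first later visit. Resting SBP, DBP and HR, and the standing-minus-resting difference, then carry a posture component that cannot be separated from time or treatment within a subject or within an arm.

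The stake is safety monitoring. Every subject has diabetic neuropathy, and Section 5.3 says it is unknown whether the drug might worsen a pre-existing neuropathy. If an autonomic effect builds up with dosing, it would be sought at the visits where the posture no longer matches baseline. There is no data safety monitoring board (Section 12), and the periodic safety reviews in Section 9.3.1 use pooled, blinded data. While the trial runs, those reviewers cannot compare arms, so change from baseline is one of their main internal references.

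**Working it through.** The plan gives no figure to reproduce. The check is a comparison of sections, followed by two short calculations on assumed values.

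**Step 1. Posture by visit** (Table 2-1, Sections 10.2.1.1 to 10.2.3, Section 10.3.3.1.5)

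| Visits | Resting posture | Followed by standing |
|---|---|---|
| V1 screening; V2 (Day 1) pre-dose | Supine | Yes |
| V2 (Day 1) post-dose | Supine | Yes |
| V3 to V7 (Days 14, 28, 42, 56, 70), before and after infusion | Sitting | Yes |
| V8, V9, V10, V11 (Days 71, 77, 84, Week 18 or early termination) | Sitting | Yes |

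Visits after Day 1 with vital signs: V3 to V11 = 9. Infusions given at those visits: 5 of 6.

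**Step 2. Is there a seated baseline?** Only the screening and Day 1 pre-dose sets precede treatment, and both are supine. Whichever is called baseline, it is supine. The first seated reading is before the Day 14 infusion, after one dose has already been given.

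**Step 3. Which quantities are affected?**

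- Resting SBP, DBP and HR, change from baseline after Day 1: sitting minus supine, so mixed.
- Standing-minus-resting difference against its pre-treatment value: sit-to-stand against lie-to-stand, so mixed.
- Standing BP and HR: standing against standing with the same timing rule. Only the preceding rest posture differs.
- Pre- to post-infusion within Days 14 to 70: sitting against sitting, so matched.
- Day 1 post-dose against Day 1 pre-dose: supine against supine, so matched.
- Temperature and respiratory rate: little concerned.

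**Step 4. Does the offset bias the comparison with placebo?** Let d be the mean posture offset, the same in all arms, and e the drug effect. The mean change is e + d on active and d on placebo, and the difference is (e + d) − d = e. With assumed e = −3 mmHg:

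- d = 0: −3 and 0, difference −3
- d = −5: −8 and −5, difference −3
- d = −10: −13 and −10, difference −3

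The within-arm figures move with d. The difference between arms does not.

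**Step 5. What could happen to sensitivity?** This is an illustration only; nothing in it except the 20 mmHg cut-off (exclusion criterion 27) comes from the protocol. Assume that the lie-to-stand SBP fall is normal with mean m and SD 10 mmHg, and that sit-to-stand reduces each fall by k. The share reaching 20 mmHg is 1 − Φ((20 − (m − k))/10). For m = 10 and k = 5 this is 1 − Φ(1.5) = 6.7%.

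| m (mmHg) | k = 0 (from supine) | k = 3 | k = 5 | k = 10 |
|---|---|---|---|---|
| 5 | 6.7% | 3.6% | 2.3% | 0.6% |
| 10 | 15.9% | 9.7% | 6.7% | 2.3% |
| 15 | 30.9% | 21.2% | 15.9% | 6.7% |

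If sit-to-stand is the milder challenge, fewer subjects in every arm cross a fixed threshold. How many fewer depends entirely on k, which the documents do not give.

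**The case against.** The strongest reply is that the trial is randomised and placebo-controlled, all arms follow the same posture rule, and safety conclusions will rest on comparison with placebo. Step 4 confirms this, and it stands. It does not help reviewers who see only pooled, blinded data during the trial, or an investigator judging one subject against that subject's own baseline.

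A second reply is that Section 13.1 is only a summary, Section 13.1.6.3 neither defines baseline nor says that postures are pooled, and the SAP can separate them. That stands for the tabulations. It does not meet the main point, because no analysis plan can supply a seated pre-treatment reading that was never taken.

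Several stronger readings are tempting, and the documents do not support them:

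- *That only Day 1 has like-for-like post-dose data.* Section 10.2.2.2 takes sitting-then-standing sets before and after each of the five later infusions.
- *That every change-from-baseline figure is distorted.* Standing readings have a standing baseline, and temperature and respiratory rate are little concerned.
- *That the stopping rule is impaired.* Section 9.3.1 acts on severe autonomic adverse events judged drug-related, not on a measured fall from supine.
- *That a planned incidence of orthostatic hypotension cannot be computed.* The 20/10 mmHg definition is an eligibility criterion only, and Section 13.1.6.3 plans no such incidence.
- *That the loss of sensitivity is known.* That sit-to-stand is the weaker challenge is a physiological inference.

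The autonomic risk is also followed through adverse events, neurological examinations and the autonomic symptoms item of the TNSn (Section 10.3.3.1.8), so detection does not depend on vital signs alone.

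**Conclusion.** The point holds as a measurement flaw of limited scope. At all nine visits after Day 1, the planned changes from baseline in resting SBP, DBP and HR compare sitting with supine, and the orthostatic change before treatment cannot be compared like-for-like with the change under repeated dosing. Within-subject and blinded pooled monitoring of a named autonomic risk is weaker than it need be, but not absent. Between-arm comparisons are not biased, provided the posture offset is common to all arms, which the shared rule makes reasonable. No numerical size can be given, since the percentages above are conditional on assumed values. The missing seated baseline follows directly from the schedule and needs no assumption. The change is worth making because it is cheap, but the flaw does not threaten the trial's conclusions.

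**What to change.** 1. For subjects still to be enrolled, add one sitting-then-standing set before dosing on Day 1, in Section 10.2.2.1, Section 10.3.3.1.5 and footnote c of the Schedule of Events. The existing supine set stays, so Day 1 post-dose readings keep their matched baseline.
2. The alternative is one resting posture at all visits. Days 28, 56, 84 and Week 18 already include ten minutes supine for the ECG. However, the study is under way and its dose arms differ by stage, so a mid-study switch would mix postures across stages. The added Day 1 set avoids this.
3. In Section 13.1.6.3, state that changes in resting BP and HR, and in the standing-minus-resting difference, are computed only against a same-posture baseline.
4. For subjects already enrolled without a seated baseline, report seated values by arm against concurrent placebo, not as change from the supine baseline.

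The cost is amendment wording and a few extra minutes on Day 1. The seated baseline cannot be recovered for subjects already enrolled, so for them only the analysis restriction helps.
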